1.1. Unmet Need

Currently, no FDA-approved treatments for anxiety disorders are designed to improve whole brain functional connectivity by targeting the angiotensin and adrenalin systems simultaneously. This is a critical research gap because anxiety disorders are 1) common, 2) debilitating, 3) co-morbid and 4) difficult to treat (Cerda M. 2010). Panic Disorder, for example, is prevalent in 6% of primary care patients (Katon W. 1986). Current FDA-approved treatments, which target symptomatology using neurotransmitter-specific approaches, are limited due to adverse reactions, including abuse potential. For example, current treatments for Panic Disorder include selective serotonin reuptake inhibitors (SSRIs), which have a small to medium effects, and benzodiazepines, which are not beneficial for long-term use due to tolerance, dependence, cognitive disturbance, and exacerbation of co-morbid mood disorders (Otto M. 1989, Edwards R. 1980). Regarding future treatments, the drugs currently being tested for Panic Disorder target mechanisms of action similar to currently approved treatments.

Whereas many of the anxiety disorders feature hundreds of novel treatment options in development, Panic Disorder represents an important disorder with fewer options in

development. There are few planned or active Phase 2 or 3 studies for the treatment of Panic Disorder in adults.

1.2. HB-1 for the Treatment of Panic Disorder

The Sponsor plans to develop a single dosage formulation therapy of verapamil and telmisartan for the treatment of Panic Disorder in adults. HB-1 contains telmisartan and verapamil, two products previously approved by the FDA for the treatment of cardiovascular conditions. Telmisartan (Micardis[®]) was approved by the FDA in 1998 and Verapamil (Verelan[®] PM) was approved in the United States in 1981. HB-1 is dosed using a specific ratio of verapamil to telmisartan which leads to its unique clinical effects. HB-1 treatment is expected to help patients achieve greater reductions in specific symptomatology, faster psychosocial advancement, and higher quality of life, with a mechanism of action related to normalization of asymmetric cerebral blood flow patterns that cause disability.

At this time, Honeybrains has conducted an IRB-approved, observational cohort study of a diverse group of neurology and psychiatry patients who received combination therapy with telmisartan and verapamil from 2019 to March 2020. The trial included a total of 102 patients, ages 18 to 70, with clinically diagnosed panic disorder, social anxiety disorder, ADHD, and other co-morbidities such as PTSD, migraine, and/or chronic musculoskeletal pain. Overall, the treatment appeared to significantly reduce symptomatology without causing adverse symptomatology or changes to vital signs. Specifically, the average self-reported symptom severity was significantly reduced in eight of the 10 cardinal neuropsychiatric symptoms (ie, anxiety, depression, irritability, apathy, body pain, insomnia, headache, cognitive difficulty) post treatment compared to baseline. Effect sizes were largest for anxiety, apathy, cognitive difficulty and overall neuropsychiatric disability. Psychosocial outcomes (NIH Toolbox General Life Satisfaction) were significantly better after combination treatment. Post-treatment systolic and diastolic blood pressure measurements did not change significantly from baseline. The effect of combination therapy on vital signs was no different than the effect of individual telmisartan or individual verapamil. The Overall Medical Review of Symptoms score was not significantly higher at one month or last observation; in fact, it was lower. Also, the rate of adverse symptoms from combination treatment was similar to known rates of adverse symptoms from verapamil and telmisartan. Importantly, the lateralization of the Weber test, which indicates the dominant side of activity of the auditory functional network, changed significantly when patients went on or off treatment, suggesting that the mechanisms of action is acting on reversible patterns of functional connectivity.

In summary, this study suggested that in terms of safety HB-1 was well tolerated, with an adverse event profile that is no different than those of the individual agents, and as a novel therapeutic agent HB-1 is hypothesized to significantly reduce disease severity in patients with panic disorder and ADHD. An extensive body of literature supports the use of this co-administration and describes relationships between psychosocial stress, the adrenergic system, functional connectivity, cerebral blood flow, angiotensin receptors and calcium channels (Kikuchi K. 2020, Jennings JR. 2009). Collectively, findings from the clinical data and from prior research suggest that treatments that normalize cerebral blood flow may lead to more complete relief of inter-related neuropsychiatric symptoms (anxiety, depression, irritability, body

pain, fatigue, headache, apathy, cognitive difficulty, psychosis, insomnia) that are germane to different neurological and behavioral health disorders.

1.3. **HB-1**

HB-1, a fixed dose combination of 96 mg telmisartan and 288 mg verapamil, two previously FDA-approved antihypertensives, is a novel therapeutic agent targeting symptoms and QoL for patients with Panic Disorder. HB-1 treatment is expected to help patients achieve greater reductions in specific symptomatology, faster psychosocial advancement, and higher QoL, with a mechanism of action related to normalization of asymmetric cerebral blood flow patterns that cause disability. HB-1 is a new treatment which modulates the brain renin angiotensin system (RAS) and adrenergic system simultaneously, resulting in a central hemodynamic that improves outcomes in different neuropsychiatric disorders. The use of treatments that target central mechanisms common to more than one co-morbidity could radically improve the quality of outcomes in neurological and behavioral disorders.

1.4. **Telmisartan**

Telmisartan, an angiotensin II type 1 receptor (AT1) blocker, is approved for the treatment of hypertension. The pro-inflammatory properties of angiotensin II as well as its anti-inflammatory effects are well-established ([Fan X. 2017](#)). Poor adaptation to stress, alterations in cerebrovascular function and excessive brain inflammation play critical roles in the pathophysiology of many psychiatric and neurological disorders ([Saavedra JM. 2012](#)). AT1 blockade may have a therapeutic effect in these types of disorders.

1.5. **Verapamil Hydrochloride**

Verapamil is a calcium channel antagonist used in cardiovascular diseases such as hypertension, angina, and certain arrhythmias. It is used clinically as a racemic mixture that contains equal amounts of (R)- verapamil and (S)- verapamil. Its antihypertensive effects result from causing a decrease in peripheral vascular resistance. It specifically blocks the L-type calcium channel along with other, lesser characterized, calcium channels (T-, P-, and possibly N- and Q-type Ca (2+) channels) ([Tfelt-Hansen P. 2009](#), [Dobrev D. 1999](#)).

P-glycoprotein function, which is involved in verapamil BBB efflux, is associated with several neurodegenerative and psychiatric diseases ([van Assema DM. 2012](#)). Measures of psychiatric morbidity in patients taking verapamil tended to improve, such as measurements of cognitive scores and psychiatric comorbidity scores ([Palmer A. 1990](#)). Multiple studies found verapamil to be well tolerated in patients with bipolar disorder with therapeutic effects in mania comparable to amitriptyline, prazosin and propranolol ([Cipriani A. 2016](#)). Other psychiatric clinical measures have shown significant improvement with verapamil therapy such as the Brief Psychiatric Rating Scale (BPRS) and general impression.

1.6. **Study Overview**

This multicenter, randomized, double-blind, placebo-controlled trial will assess the safety of HB-1 and effectiveness of HB-1 versus placebo for the treatment of Panic Disorder. This study will enroll approximately 80 patients who meet DSM-5 criteria for the diagnosis of Panic Disorder recruited from approximately eight clinical research sites. All patients will receive an oral dose

of HB-1 or matching placebo once a day. HB-1 is a proprietary combination of telmisartan and verapamil in a once-daily, extended release formulation.

2. OBJECTIVES

2.1. Primary Objective

To determine the safety and efficacy of HB-1 versus placebo in male and female adult patients aged 18 to 60 years, inclusive, with Panic Disorder.

2.2. Exploratory Objective

To compare the effectiveness of HB-1 on Common Neuropsychiatric Co-Morbidities.

3. ENDPOINTS

3.1. Safety Endpoints

Incidence of Treatment Emergent Adverse Events (TEAEs), clinically significant changes in clinical laboratory values, changes in electrocardiogram (ECG), and Columbia Suicide Severity Rating Scale (C-SSRS) ([Oquendo MA 2003](#)), and orthostatic vital signs.

3.2. Efficacy Endpoints

- Change in Panic Disorder Symptom Severity Scale (PDSS) ([Furukawa T. 2009](#)) - primary efficacy endpoint.
- Number of panic attacks
- Change in Clinical Global Impression-Severity Scale (CGI-S) ([Guy W. 1976](#))
- Change in Quality of Life Enjoyment and Satisfaction Questionnaire Short Form (Q-LES-Q-SF) ([Endicott J. 1993](#))
- Change in Leibowitz Anxiety Scale (LSAS) ([Heimberg R. 1999, Baker S. 2002](#))
- Change in Assessment of Overall Sleep Quality -- Question #6 from the Pittsburgh Sleep Quality Index ([Buysse DJ. 1989](#))

3.3. Exploratory Endpoints

- Change in Toronto Alexithymia Scale (TAS-20) ([Bagby R. 2020](#))
- Change in Hamilton Anxiety Rating Scale (HAM-A) ([Bech P. 1990](#))
- Change in Montgomery-Asberg Depression Rating Scale (MADRS) ([Fantino B., Moore N. 2009](#)) only for patients with a medical history of depression
- Change in CogScreen Symbol Digit Coding test (SDC) ([Kay G. 1995](#))
- Change in Conners' Adult ADHD Rating Scale (CAARS) ([Walls B. 2017](#)) only for patients with a medical history of ADHD
- Change in The PTSD Checklist for DSM-5 ([Blake DD. 1995, Blevins CA. 2015](#)) only for patients with a medical history of PTSD

- Change in Short Form McGill Pain Questionnaire (SF-MPQ) ([Melzack R. 1987](#)) only for patients with a medical history of chronic pain
- Change in Migraine Disability Assessment Questionnaire (MIDAS) ([Lipton RB. 2001](#)) only for patients with a medical history of migraine

4. STUDY DESIGN AND DESCRIPTION

[figure not shown]
4.1. Study Design

This is a multicenter, randomized, double-blind, placebo-controlled trial. All patients with Panic Disorder, with or without specified co-morbidities, who meet all of the inclusion and none of the exclusion criteria will be eligible. Patients and researchers will be blinded to their treatment group.

Approximately 80 patients with Panic Disorder will be enrolled and randomized in a 1:1 ratio to HB-1 or placebo using a central randomization.

The study design is presented in [Figure 2](#). A schedule of assessments is presented in [Table 1](#).

Figure 2: Study Design

4.2. Justification for Study Design, Dose, and Endpoints

This study was designed as a pragmatic trial because in real-world conditions most panic disorder patients have multiple neuropsychiatric co-morbidities and are usually taking one or more medications. Pragmatic trial design was chosen because pragmatic trials are useful to

address questions related to generalizability and variability in response. Pragmatic trials can be useful to evaluate the effectiveness of an intervention in real-world setting, ie, in patients who may not be adherent to treatment and/or who have co-morbid conditions. Pragmatic trials focus on a wide range of outcomes, such as symptoms, mechanisms, functional status, quality of life, and costs.

A pragmatic study design that enables wider inclusion of patients, regardless of whether they have co-morbidities, or are already on treatment, was also important in order to increase the recruitability of patients (reduce exclusionary criteria). A pragmatic design is enabled by the fact that the drug does not interact with most common psychiatric treatments.

4.3. Dosing Frequency

HB-1 and placebo are dosed once a day (QD), nightly at bedtime (QHS) with or without food.

4.4. Monitoring of Adverse Events

Safety will be assessed through the monitoring of Adverse Events (AEs), Treatment Emergent Adverse Events (TEAEs), clinical laboratory assessments, ECGs, Columbia Suicide Severity Rating Scale (C-SSRS) ([Oquendo MA 2003](#)), and orthostatic vital signs. Patients will be monitored for safety from the first dose of HB-1 or placebo at study Week 0 through the Safety Follow-up visit. Serious adverse events (SAEs) will be reported immediately to the sponsor and recorded in the eCRF.

Table 2 below provides guidance on the management of known toxicities that have been associated with verapamil or telmisartan monotherapy. If any of the following criteria are met, the subject will have study treatment discontinued and the Medical Monitor must be informed immediately. Subjects may discontinue study treatment, however, and remain in the study (see [Section 4.5](#)). The stopping criteria listed below will also be captured as adverse events (see [Section 8](#)).

Table 2: Subject Specific Stopping Criteria

Cardiac Disorders	
Hypotension	
 SBP <90 mmHg and DBP <60 mmHg for three consecutive readings 10 minutes apart
Orthostatic Hypotension	
 Decline of ≥ 20 mm Hg in systolic or ≥ 10 mm Hg in diastolic blood pressure after 3 minutes of standing.
New-onset 2 nd or 3 rd degree AV block	
 Grade 1 or higher per CTCAE V5.0*
Sick sinus syndrome	
 Grade 1 or higher per CTCAE V5.0
Atrial flutter	
 Grade 1 or higher per CTCAE V5.0
Atrial fibrillation	
 Grade 1 or higher per CTCAE V5.0
New-onset bradycardia	
 Resting heart rate below 50
New-onset tachycardia	
 Resting heart rate above 120

Onset of angina pectoris	
 Grade 1 or higher per CTCAE V5.0
Congestive heart failure	
 Grade 1 or higher per CTCAE V5.0
Pulmonary edema	
 Grade 1 or higher per CTCAE V5.0
Peripheral edema	
 Grade 2 or higher per CTCAE V5.0
General Disorders	
Urticaria	
 Grade 2 or higher per CTCAE V5.0
Hyperkalemia	
 Potassium values that are 2X the ULN for the local lab normal reference ranges. Values may be repeated and confirmed.
Gout exacerbation	
 Hyperuricemia Grade 1 or higher per CTCAE V5.0 Values may be repeated and confirmed.
Impaired hepatic function	
 ALT, AST, ALP values that are twice the upper or lower limit of local lab normal reference range. Values may be repeated and confirmed.
Impaired renal function	
 Doubling in creatinine value. Values may be repeated and confirmed.
Thrombocytopenia	
 Platelet count values below 150,000/mL Values may be repeated and confirmed.

*Common Terminology Criteria for Adverse Events (CTCAE) V5 dated 27Nov2017

Women who are using oral contraceptives will be monitored for adverse events associated with overexposure at each study visit. This should include signs and symptoms of myocardial infarction, stroke, and venous thromboembolism.

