5.2. Exclusion Criteria

Patients are to be excluded from the study if they meet any of the following criteria:

1. Severe uncontrolled cardiac disease within 6 months of Screening, including but not limited to uncontrolled hypertension, hypotension (defined as below 90/60); unstable angina; myocardial infarction (MI) or cerebrovascular accident (CVA).
2. Any clinically significant electrocardiogram (ECG) abnormalities at screening.
3. History of atrial flutter, atrial fibrillation or hypertrophic cardiomyopathy.
4. Inadequate hepatic function defined as total bilirubin $>1.5 \times$ the upper limit of normal (ULN) ranges of each institution, aspartate aminotransferase (AST) and alanine aminotransferase (ALT) $>3 \times$ the ULN range of each institution.
5. Inadequate renal function defined as serum creatinine $>1.5 \times$ the ULN range of each institution and/or eGFR <60 .
6. Any clinically significant abnormalities in clinical laboratory assessments as assessed by the investigator.
7. Any other systemic conditions or organ abnormalities that in the opinion of the Investigator may interfere with the conduct and/or interpretation of the current study.
8. Unable to complete neuropsychological testing.
9. Diagnosis of Bipolar I, Bipolar II disorder or Schizophrenia.
10. History of suicidal behaviors including ideation.
11. Current treatment with doses of benzodiazepines that are outside the FDA-approved prescriber's information.
12. Use of tricyclic antidepressants and monoamine oxidase inhibitors (MAOIs) is prohibited.
13. Already on treatment with either telmisartan or verapamil or both.
14. Documented prior drug allergy to either telmisartan or verapamil.
15. Documented contraindication to taking telmisartan or verapamil (eg, Duchenne's muscular dystrophy, myasthenia gravis).
16. Documented moderate to severe substance abuse within the last 6 months (recreational cannabis use is allowed).
17. Pregnant or breastfeeding.

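### The liver stopping rule in Protocol Table 2 can stop an eligible patient whose enzymes have not changed, and its lower-limit wording is a drafting error

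*Protocol*

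**What the plan says.** Protocol 4.4 introduces Table 2 as guidance on known toxicities of the two drugs, but the next sentence is binding: "If any of the following criteria are met, the subject will have study treatment discontinued". The laboratory rows include:

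- Liver: "ALT, AST, ALP values that are twice the upper or lower limit of local lab normal reference range".
- Gout: "Hyperuricemia Grade 1 or higher per CTCAE V5.0".
- Platelets: "Platelet count values below 150,000/mL".
- Potassium: "Potassium values that are 2X the ULN for the local lab normal reference ranges".
- Kidney: "Doubling in creatinine value".

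Each of these rows allows, but does not require, a repeat test. SAP 6.11 carries the liver, gout and platelet rows in the same words.

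On entry, exclusion 4 in Protocol 5.2 removes patients with "aspartate aminotransferase (AST) and alanine aminotransferase (ALT) $>3 \times$ the ULN range of each institution". It gives a bilirubin limit but none for ALP. Exclusions 6 and 7 leave other laboratory abnormalities and organ conditions to the investigator's judgement. Protocol 6.1.8 and SAP 6.10.3 list the scheduled laboratory tests item by item.

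**The concern.** A stopping rule for drug toxicity should respond to something that happens on treatment. The liver row responds to an absolute level, and that level lies below the level at which AST and ALT bar entry. So the plan can admit a patient and then require the site to stop treatment for a value that was there at entry and has not moved. The reference to the lower limit adds a second fault, because no reading of it describes liver injury.

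At stake are avoidable treatment stops and sites left to decide for themselves which parts of a mandatory rule to ignore. Two secondary rows share part of the problem. The gout row relies on a blood result that the schedule never produces. The platelet row has no change condition, and no entry criterion limits the platelet count.

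**Working it through.** There is no plan figure to reproduce here. The check compares thresholds.

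**Liver, upper limit.** Let b be the patient's pre-dose value in multiples of ULN. Exclusion 4, read as applying to either enzyme, admits b ≤ 3 for AST and ALT, and any b for ALP. The stop rule is met at 2 or more. The overlap is 2 ≤ b ≤ 3 for AST and ALT, and all b ≥ 2 for ALP. (If exclusion 4 is read literally as needing both enzymes above 3, the overlap is wider.)

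The rise needed to trigger the present rule is max(2/b, 1). Under the rule proposed below, the limit is 2 for b ≤ 1 and 2b for b > 1, with an example ceiling of 5:

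| b (× ULN) | Present limit | Rise needed now | Proposed limit | Rise needed then |
|---|---|---|---|---|
| 0.5 | 2 | 4-fold | 2 | 4-fold |
| 1 | 2 | 2-fold | 2 | 2-fold |
| 1.5 | 2 | 1.33-fold | 3 | 2-fold |
| 1.9 | 2 | 1.05-fold | 3.8 | 2-fold |
| 2 | 2 | none | 4 | 2-fold |
| 2.5 | 2 | none | 5 | 2-fold |
| 3 | 2 | none | above 5 (6 without the ceiling) | 5/3 = 1.67-fold |

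Repeat testing does not help, since repeating a stable value confirms it.

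**Liver, lower limit.** Twice the lower limit of normal (LLN) lies inside the normal range whenever ULN > 2 × LLN. The documents give no local ranges. With assumed ranges of 7–56 (ALT), 10–40 (AST) and 40–130 U/L (ALP), twice the lower limit is 14, 20 and 80 U/L, all normal.

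**Gout.** The scheduled list has 15 metabolic panel items, 11 blood count items and 8 urinalysis items: 15 + 11 + 8 = 34. None is uric acid, in either document.

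**Change conditions.** Of the five laboratory rows (potassium, gout, liver, kidney, platelets), only the kidney criterion requires a change in the patient's own value. Among the cardiac rows, AV block, bradycardia and tachycardia must be new in onset. So the table already uses the device that the liver and platelet rows lack. The potassium row lacks it too, but twice ULN is not a plausible stable entry value. The platelet remark assumes that the count is meant per microlitre. As printed, 150,000/mL would be 150,000/1,000 = 150 per microlitre, which may be an artefact of text extraction and is not counted as a fault.

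**Number of patients.** The documents give no prevalence of stable values at 2–3 × ULN. Assuming 0.5%, 1% or 2.5%: 80 × 0.005 = 0.4, 80 × 0.01 = 0.8 and 80 × 0.025 = 2 patients, both arms together.

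**The case against.** The strongest reply is that the overlap is small and mostly theoretical. Exclusions 6 and 7 let the investigator turn away a patient with raised enzymes, the row is labelled as impaired liver function so no site would stop a patient for a normal value, and the rule errs towards caution. Much of this stands. The discretionary exclusions narrow the overlap, but they set no number and do not close it. The lower-limit wording is almost certainly a slip, though it is in both documents.

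On gout, the row label speaks of an exacerbation, and a flare could prompt an unscheduled uric acid test. That is fair: the row needs clarifying, and the claim that it can never be met would be wrong.

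Two stronger inferences are tempting and should not be drawn.

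- *A Week 0 sample could stop a patient before any drug is taken.* Section 4.4 sets safety monitoring from the first dose and presents Table 2 as management of drug toxicity, so the context already implies on-treatment values.
- *Stable values will be forced into the adverse event tables.* Section 4.4 does say "The stopping criteria listed below will also be captured as adverse events", but it then refers to Section 8. There, 8.1.1 excludes a pre-existing condition that has not worsened, and 8.1.2 keeps such values out of the treatment-emergent events.

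**Conclusion.** The liver row is wrong as written. For AST or ALT between 2 and 3 × ULN, and for ALP at or above 2 × ULN, an eligible patient meets a mandatory stop with no worsening, and *or lower* should not be there. This follows from the text alone, given that the investigator has not used exclusions 6 or 7. The gout and platelet points are secondary.

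The effect is minor: on the assumed prevalences, 0.4 to 2 of 80 patients, stopped in the cautious direction. A reader might go on to infer bias in the primary PDSS comparison. The documents do not support that: patients who stop treatment may remain in the study and continue efficacy assessments (Protocol 4.5), and SAP 7.10 plans a treatment policy strategy for all intercurrent events. The case for acting is that a mandatory threshold gives a wrong answer when followed, and correcting it costs almost nothing.

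**What to change.** 1. **Liver row, both documents.** Delete *or lower* and reword along these lines: on-treatment ALT, AST or ALP at least 2 × ULN and, if the pre-dose value was above ULN, at least 2 × the pre-dose value; or any of the three above an absolute ceiling whatever the baseline. The ceiling is for the medical team to set (5 × ULN is an example) and must cover ALP, which otherwise would have no upper stop limit because it has no entry limit. Keep repeat testing optional, so that stopping is not delayed for patients with normal baselines.
2. **Gout row.** Define the trigger as a clinical gout flare, with uric acid tested on suspicion.
3. **Platelet row.** Require the low count to be new or worsened from the pre-dose value.

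The cost is wording in three rows of Table 2 and the SAP copy, with no added visit or scheduled sample. The limit stays at 2 × ULN for every patient who enters at or below ULN. The downside is somewhat less conservative stopping for those who enter above it (3 × ULN from a baseline of 1.5, 4 × ULN from a baseline of 2). This is bounded by the ceiling and by the investigator's freedom under 4.5 to stop treatment on medical grounds. A patient admitted with ALP already above the ceiling would still be stopped without worsening, and the medical team should accept that knowingly when setting the figure.

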6.1.8. Clinical Laboratory Tests

The following laboratory parameters will be measured at the time points specified in the Schedule of Assessments ([Table 1](#)) and will be analyzed locally:

- Pregnancy test should be administered for women of child-bearing potential (WOCBP) within 7 days prior to Week 0 and then at each subsequent study visit.
- Comprehensive Metabolic Panel (CMP): albumin, blood urea nitrogen, calcium, carbon dioxide, chloride, creatinine, creatinine phosphokinase, glucose, potassium, sodium, total bilirubin, total protein, alanine aminotransferase (ALT), alkaline phosphatase (ALP), aspartate aminotransferase (AST)
- Complete Blood Count (CBC): white blood cell count, red blood cell count, hematocrit, hemoglobin, mean corpuscular volume (MCV), mean corpuscular hemoglobin (MCH), mean corpuscular hemoglobin concentration (MCHC), red cell distribution (RDW), platelet count, mean platelet volume (MPV), Vitamin B12
- Urinalysis: microscopic examination, specific gravity, pH, protein, glucose, ketones, blood and urobilinogen

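### The liver stopping row in both tables names the lower limit of normal as well as the upper; the lower-limit part works on neither reading and should be deleted

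*Protocol*

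**What the plan says.** The impaired hepatic function row of Protocol Table 2 (Section 4.4) sets the stop at "ALT, AST, ALP values that are twice the upper or lower limit of local lab normal reference range" and adds that values may be repeated and confirmed. The row in SAP Section 6.11, Table 2, is worded identically. SAP Section 8, which lists changes from the protocol, does not mention it.

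The text above the protocol table opens softly: "Table 2 below provides guidance on the management of known toxicities that have been associated with verapamil or telmisartan monotherapy". The sentence after that is mandatory: "If any of the following criteria are met, the subject will have study treatment discontinued and the Medical Monitor must be informed immediately". Section 4.4 also says: "The stopping criteria listed below will also be captured as adverse events".

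Other places bear on the meaning. The hyperkalemia row of the same table uses only the upper limit: "Potassium values that are 2X the ULN for the local lab normal reference ranges". Exclusion 4 (Protocol Section 5.2) defines inadequate hepatic function by multiples of the ULN alone: bilirubin above 1.5 × ULN, and AST and ALT above 3 × ULN. Protocol Section 6.1.8 says that laboratory parameters are measured at the scheduled time points "and will be analyzed locally". Neither document gives a numerical reference range.

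**The concern.** This row decides whether a patient stays on treatment, so it should yield one threshold. It names two limits and gives no direction for the second. The lower-limit part could mean a value of at least 2 × LLN, or a value of half the LLN or less, and neither is a sensible liver stop.

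What is at stake is consistency. A site or monitor who reads the row literally could stop treatment without need, record an adverse event for a normal enzyme value, or query a supposedly missed stop. About 8–10 sites use their own laboratories, so nothing in the text ensures that all of them resolve the ambiguity in the same way.

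**Working it through.** The plan gives no number to reproduce here, so the check is a reading of the text plus threshold arithmetic.

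**Inputs.** The row wording comes from Protocol Table 2 and SAP Table 2, and the entry limit from Exclusion 4. The ratio R = ULN/LLN is not in the documents. It is an assumption, shown over a range.

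**Step 1: at least 2 × LLN.** Because LLN is below ULN, any value at or above 2 × ULN is also at or above 2 × LLN. The combined rule therefore reduces to 2 × LLN, and the upper-limit part adds nothing. Expressed on the ULN scale:

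2 × LLN = (2/R) × ULN.

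This falls inside the normal range when 2/R < 1, that is, when R > 2. The share of the reference interval's width lying above 2 × LLN is

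(ULN − 2 LLN)/(ULN − LLN) = (R − 2)/(R − 1), set to 0 when R ≤ 2.

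| Assumed R | 2 × LLN as a multiple of ULN | Share of interval width above 2 × LLN |
|---|---|---|
| 1.5 | 2/1.5 = 1.33 | 0 |
| 2 | 2/2 = 1.00 | 0 |
| 2.5 | 2/2.5 = 0.80 | 0.5/1.5 = 33% |
| 3 | 2/3 = 0.67 | 1/2 = 50% |
| 4 | 2/4 = 0.50 | 2/3 = 67% |

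The last column gives shares of the interval, not of patients. It shows where the threshold falls, not how often it would be met.

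**Step 2: half the LLN or less.** This would stop treatment for low enzymes. It does not fit the row's own heading, a table of known toxicities, or Exclusion 4, which looks only upward.

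**Step 3: conventions elsewhere in the table.** Low-side stops are written with an explicit direction. The bradycardia row says "Resting heart rate below 50", the platelet row also uses a below-type wording, and the hypotension row uses a less-than sign. The form varies and all of these are absolute cut-offs, so this is weak support. The hyperkalemia comparison is weak too, because hyperkalemia can only be a high value. The case rests on Steps 1 and 2.

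**Step 4: exposure.** The laboratory row of the SAP schedule (Section 6.5) has four marks: screening, baseline, Week 2 and one at the end. Table columns have shifted in the text available to me. The Weber test row has its last mark in the same place, and Protocol Section 6.1.12 puts that test at Week 12. On that alignment the last laboratory mark is also Week 12, when treatment ends. Week 2 is then the only scheduled post-baseline laboratory visit at which the row could shorten treatment, unscheduled tests aside. The protocol's copy of the row also has four marks but cannot be aligned reliably, so this is a probable reading rather than a certain one.

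**Step 5: the ULN multiple against entry.** Exclusion 4 removes patients only above 3 × ULN for AST and ALT. Take an example patient with AST at 2.5 × ULN. Since 2.5 ≤ 3, Exclusion 4 does not apply; since 2.5 ≥ 2, the stopping row is already met. Exclusion 6 (abnormalities the Investigator judges clinically significant) might remove such a patient, but that is a judgement, not a limit. Exclusion 4 sets no limit for ALP. This conflict needs no assumption about reference ranges.

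**The case against.** The strongest reply is that no competent site would apply the lower-limit part. The row is headed as impaired hepatic function, a reading that stops patients with normal enzymes defeats itself, and 2 × ULN is the obvious intention. If every site applies 2 × ULN, the extra words add no stops at all. This stands as an argument about size. It does not make the text correct, because it relies on sites departing from the approved wording of a mandatory rule.

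Three further defences carry less weight. Calling the table guidance does not soften the sentence that requires discontinuation. Repeating a test confirms a number but does not say which threshold applies. The Medical Monitor's ongoing blinded review (Protocol Section 8) may reveal a misapplied stop, but only after the event.

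A reader might infer that many patients with normal liver tests will be taken off treatment. The documents do not support that: they contain no reference ranges and no sign that any site would use 2 × LLN, and the scheduled exposure appears to be a single visit. A reader might also infer damage to the efficacy result. That is not supported either. Patients who stop treatment may remain in the study and continue efficacy assessments (Protocol Section 4.5), SAP Section 7.10 plans a treatment policy strategy, and no SAP analysis uses the row. That the wording is a drafting slip is itself an inference about intent, though a likely one.

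**Conclusion.** The lower-limit part is wrong as written in both documents. This follows from the wording and from LLN being below ULN. That it captures normal values depends on the local laboratory's ULN exceeding 2 × LLN, which the documents neither confirm nor exclude.

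The size is small and cannot be put as a number of patients. If sites apply 2 × ULN, as is probable, the effect is nil. Otherwise it would be occasional unnecessary stops and adverse event entries, mostly around Week 2 if the schedule is read as above. Adverse events are only summarised descriptively, so no formal test would change. The appearance of the same sentence in the SAP adds no statistical weight, since the SAP only repeats the table. I rate this a minor wording correction to a safety threshold.

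**What to change.** In Protocol Table 2 and SAP Table 2, delete the words *or lower* and state a single threshold, for example: *ALT, AST or ALP at or above 2 × ULN of the local laboratory range; values may be repeated and confirmed.*

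In the same amendment, the sponsor's medical lead should reconcile the multiple with Exclusion 4, so that an eligible patient does not already meet the stop at entry. Either the entry limit or the stopping multiple can move; that is a medical decision.

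The change can go in the next protocol amendment, with the IRBs informed as Protocol Section 10.4 requires and the SAP table updated to match. I would not issue a separate interim instruction: one that narrows the stop while the approved text stands would leave sites unsure which governs.

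The cost is two words in two tables, one medical decision, and IRB handling at about 8–10 sites that the amendment would need anyway. There are no added patients, visits or tests.
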